## 7.2 Study Procedures

### RCT

M	B	3	6	9	1	M
E	a	M	M	M	2	o
A	s	C	V	C	M	n
S	e	n	e	n	V	t
U	V	l	b	l	e	h
R	e	i	+	i	b	l
E	b	n	F	n	+	y
M	+	e	T	e	F	C
E	F	F			T	n
N	T			F		l
T	F					i
S						n
						e
M						
A						
I						
N						
O						
U						
T						
C						
O						
M						
E						
S						
A	X	X	X			
e						
r						
o						
b						

i c F i t n e s s ( i n - p e r s o n )	P h y s i c a l A c t i v i t y b y A c c e l e r o n e m e t r y ( m a i l e d )	X n e n t S c a l A t t e n d a n c e S E C O N D A R Y D E P	X n e n t X X	X n e n t X X		
M E D I A T C R S		E N D E N T M A R				

P	X	X	X
R			
E			
T			
I			
-			
Q			
A	X	X	X
F			
F			
E			
X			
X			
C	X	X	X
o			
n			
p			
e			
t			
i			
v			
e			
n			
e			
s			
s			
T	X	X	X
o			
b			
a			
c			
c			
c			
o			
U			
s			
e			
E	X	X	X
x			
e			
r			
c			
i			
s			
e			
S			
e			
l			
f			
-			
E			
f			
f			
i			
c			
a			
c			
y			

\* Participants among the 2019 cohort who are unable to attend the 6-month and 12-month in-person visit due to extreme circumstances will not complete the aerobic fitness test, physical activity by accelerometry, body weight, or blood pressure. These participants will complete the other measures via REDCap surveys online. (See 7.2.15). Additionally, participants among the 2019 cohort who opt to continue the study following a prolonged exercise session cancellation period due to either a disease outbreak or Penn State University recommendation to stop all exercise sessions will not complete the listed main outcomes measures, mediators, secondary dependent variables, or the covariates and other variables. These participants will complete injury-related measures via REDCap surveys online. Participants among the 2021 cohort, including those who opt to continue their study participation beyond the 12-month time point following an unforeseen, COVID-19 related exercise session cancellation period, will complete the listed 9- and 12-month measurements at the 3- and 6-month post-cancellation time points, respectively.

### Feasibility Studies – Adolescent, Major Depressive

MEASUREMENTS	Baseline	4 weeks	8 weeks
MAIN OUTCOME			
Physical Activity by Accelerometry	X	X	X
SECONDARY OUTCOMES / COVARIATES			
Physical Activity Enjoyment Scale	X	X	X
Program Attendance	X	X	X
Physical Activity Related Injuries		X	X
Loneliness	X	X	X
Depression, Anxiety	X	X	X
Program Satisfaction		X	X
Basic Psychological Needs Satisfaction	X	X	X
Sociodemographics	X		
PMC-C *	X	X	X
PSS-10 *	X	X	X
GAD-7 *	X	X	X
PHQ-9 *	X	X	X
WHODAS 2.0 *	X	X	X
BREQ-3 *	X	X	X
PESS *	X	X	X
EMGI *	X	X	X
LCE *	X	X	X

\* Measure is specific to the Major Depressive Feasibility Study.

### Feasibility Studies – Older Adult

MEASUREMENTS	Baseline	6 weeks	12 weeks
MAIN OUTCOME			
Physical Activity by Accelerometry	X		X
SECONDARY OUTCOMES / COVARIATES			
Aerobic Fitness (in-person)	X		X
Blood Pressure (in-person)	X		X
Body Weight (in-person)	X		X
Berg Balance Scale (in-person)	X		X
5X Sit-to-Stand (in-person)	X		X
Physical Activity Enjoyment Scale	X		X
Program Attendance	X		X
Physical Activity Related Injuries		X	X
Loneliness (PROMIS-29)	X		X
Depression, Anxiety (PROMIS-29)	X		X
Physical Function (PROMIS-29)	X		X
Program Satisfaction		X	X
Basic Psychological Needs Satisfaction	X		X
Sociodemographics	X		
PMC-C	X		X

#### **7.2.1 Train fitness instructors on PlayFit and Group Fitness protocols.**

The training and oversight of instructors will be led by a Consultant, an exercise physiologist faculty member at Penn State with extensive experience developing, leading, and evaluating aerobic fitness programs [47, 79]. The Consultant, an exercise physiologist who creates and tests new fitness programs for Les Mills (New Zealand), the creator of Body Pump™ and other widely used programs [47, 79], will create a Group Fitness Program that is of the same MET level and duration as PlayFit. In PlayFit, the instructor gets involved in the gameplay, which helps them to create and model a non- competitive culture of play, which is similar to how a group fitness instructor exercises in sync to group fitness participants. Leaders will also be trained by research study staff on safety procedures for minimizing injuries, both orthopedic and cardiac events. The Consultant will not have access to PHI though will review summarized adherence data.

#### **7.2.2 Rent space to hold exercise sessions.**

We will visit all indoor sports facilities in our region to find times that can be reserved for our participants to exercise. The goal is to mimic a fitness center membership in the participant's community. Few people are willing to travel far for a fitness center membership so reserving space in communities will be essential to minimizing the burden of travel. We will consider hosting the program in any indoor or outdoor space that that will suit either of the programs. These will include, but not be limited to, church-owned gymnasiums, privately owned gymnasiums and outdoor public or private spaces (e.g., parks, schools).

#### **7.2.3 Recruit participants**

## RCT

We will use mailed letters targeting adults 18+ living within 15 miles of the study site, using addresses from a marketing company, such as Modern Postcard and will mail the same letters to patients who receive primary care from either the Department of Family and Community Medicine or the Department of Medicine at Penn State Hershey. Our primary care surveys show that 59.1% of young and middle-aged adults whom we expect to be most interested, were interested in PlayFit. Of note, interest in PlayFit did not differ by gender or BMI, with 57.4% of obese patients interested versus 62.9% and 58.9%, respectively, of overweight and normal weight patients interested ( $P>.05$ ) [61], increasing the pool of potential participants.

## HOUSEHOLD MEMBER:

The same recruitment procedures will be used for RCT participants above.

## FEASIBILITY STUDY:

We will use mailed letters to patients of Penn State Health, and we may use addresses from a marketing company, such as Modern Postcard, as we are in the RCT. For the adolescent feasibility study we will send letters to parents of children aged 10-12. For the feasibility study of adults aged 51-70, we will send letters to adults in that age range. For the feasibility study of adults being treated for major depressive disorder, we will send letters to adults 18+. We know that rates of depression among clinical adult populations to be 6% among men and 12% among women, so we anticipate needing more letters for this population.

### **7.2.4 Screening for eligibility.**

The screening will be completed over the phone. Patients and household members who call will be screened by a research assistant based on the eligibility criteria (see attached screener). If the patient is eligible, we will schedule their baseline visit.

### **7.2.5 Physician Permission.**

#### RCT

Before the baseline visit, which will include a maximal exercise test, a permission form (attached) will be sent to the primary care provider for signature. The permission form for household members will not include mention of the exercise testing, as this will not be part of their participation.

#### FEASIBILITY STUDIES: Older Adult

Before the baseline visit, which will include a submaximal exercise test, a permission form (attached) will be sent to the primary care provider for signature.

#### FEASIBILITY STUDIES: Adolescent, Major Depression

Permission will be required for potential participants with between 2 and 4 risk factors for heart disease, of the following 5 (sedentary lifestyle, smoking, high blood pressure, high cholesterol, early heart disease in a family member).

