**Blood Pressure.** Blood pressure will be assessed according to the recommendations of the American Heart Association [14]. Resting blood pressure will be measured with the participant in a seated position using a professional, calibrated, aneroid sphygmomanometer. The average of three blood pressure measurements will be recorded, as our team has done in other studies [15].

**5X Sit-to-Stand.** The 5X Sit-to-Stand (5XSTS) will be administered by research study personnel at both the baseline and 12-week time points in the Older Adult Feasibility Study. Study subjects will be requested to perform the 5XSTS test as a measure of functional lower extremity strength.

**Berg Balance Scale.** The Berg Balance Scale (BBS) will be administered by research study personnel at both the baseline and 12-week time points in the Older Adult Feasibility Study. Study subjects will be requested to perform the 14-item BBS test as a measure of static balance and fall risk among older adults.

**3-Minute Step Test.** The YMCA 3-Minute Step Test (3MST) will be administered by research study personnel at both the baseline and 12-week time points in the Older Adult Feasibility Study. Study subjects will be requested to perform the test as a measure of cardiorespiratory fitness among older adults.

**Physical Function.** The 4-item, PROMIS Physical Function Questionnaire will be administered via automated, online REDCap online survey at both the baseline and 12-week time points in the Older Adult Feasibility Study.

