#### Feasibility Study:

- Age 10-12 and in the 6th or 7th grade for Adolescent Feasibility Study
- Age 51-70 for Older Adult Feasibility Study.
- Age 18+ being treated (medicines or talk therapy, as in Mental Health History Measure) for major depressive disorder (MDD) and with at least mild levels of depression (score of  $\geq 8$ ), as measured by the Hamilton Rating of Depression (HAM-D), for Major Depression Feasibility Study
- For the Major Depressive Disorder feasibility study, all participants will be required to be categorized as Sedentary, defined as less than 90 minutes of moderate or vigorous activity each week. This will be determined using Physical Activity items from the National Health Interview Survey [75].
- For the Older Adult feasibility study, all participants will be required to be categorized as Sedentary, defined as less than 60 minutes of moderate or vigorous activity each week. This will be determined using Physical Activity items from the National Health Interview Survey [75].
- For the Adolescent feasibility study, all participants will be required to be categorized as Sedentary, defined as less than 60 minutes of moderate or vigorous activity each day. This will be determined using Physical Activity items from the National Health Interview Survey [75].

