## Feasibility Study

- Physician, Nurse Practitioner or Physician's Assistant is unwilling to sign permission for subjects with between 2 and 4 risk factors for heart disease, of the following 5 (sedentary lifestyle, smoking, high blood pressure, high cholesterol, early heart disease in a family member), or unwilling to sign permission for potential subjects who disclose any of the following COVID-19-specific items during screening (family member with current or past COVID-19 infection, moderate-to-severe asthma, takes medication for or has a medical condition that weakens the immune system, symptoms of COVID-19 infection).
- A history of Heart disease, diabetes, angina, heart failure, stroke, mini-stroke (transient ischemic attack), weak or failing kidneys
- Symptoms of chest pain, dizziness, loss of consciousness, a bone or joint problem that can be worsened with physical activity or being diagnosed with a heart condition by a doctor, based on questions from the Physical Activity Readiness Questionnaire (PAR-Q) [76]
- Inability to read and speak English.
- Pregnant or planning to become pregnant in the next four (4) months.
- Planning to have surgery or move in the next four (4) months.
- Suicidality, schizophrenia, psychosis or bipolar disease, among subjects in the feasibility study for subjects with major depressive disorder (MDD), based on a affirmative response (>0) to question 3 on the Hamilton Rating Scale for Depression (HAM-D) [27].

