### Feasibility Study

Interested subjects will be screened by phone by research staff who will read the phone screening document which will ensure eligibility and will inform them of study procedures. If eligible and interested in participating, they will be asked to sign consent electronically prior to attending the initial in-person visit.

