#### FEASIBILITY STUDIES: Adolescent, Major Depression

Prior to the initial in-person visit, participants (and at least one parent in the case of the adolescent feasibility study) will review the consent form via phone call with study staff for 30 minutes. During that time, they will explain the study and complete the informed consent procedures. Of note, potential participants for the Adolescent Feasibility Study will be requested to sign consent upon arrival at the project site, prior to the beginning of any research-related activities. At the initial in-person visit, they will provide an explanation about how and when to wear the accelerometer. After the informed consent procedures are complete, research staff will send participants the following questionnaires, via a link to REDCap online and based on the target population:

Adolescents: Shortened Physical Activity Enjoyment Scale (S-PACES), Basic Psychological Needs Satisfaction, the PROMIS Depression and Anxiety Scale, Brief Loneliness Scale, PMC-C and Sociodemographics.

Adults with Major Depressive Disorder: Physical Activity Enjoyment Scale (PACES), Hamilton Rating Scale for Depression (HAM-D), Sociodemographics, PMC-C, Brief Loneliness Scale, the PMC-C, PSS-10, GAD-7, PHQ-9, WHODAS 2.0, BREQ-3, PESS, EMGI, and the LCE. Of note, the HAM-D will be completed over the phone, by either [name], a clinical psychologist, or a research staff member trained by [name], rather than being completed online.

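### The feasibility cardiac rule requires provider permission at two to four of five risk factors, but not at all five

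*Combined protocol and SAP*

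**What the plan says.** Section 7.2.5 (Physician Permission), for the Adolescent and Major Depression feasibility studies: "Permission will be required for potential participants with between 2 and 4 risk factors for heart disease, of the following 5". The five factors are sedentary lifestyle, smoking, high blood pressure, high cholesterol and early heart disease in a family member.

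Section 3.2 (Exclusion Criteria, Feasibility Study) excludes a person whose provider is "unwilling to sign permission for subjects with between 2 and 4 risk factors for heart disease, of the following 5". The other cardiac exclusions in that list rest on disease history and on symptoms or diagnoses from the PAR-Q. None uses the number of risk factors.

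Section 3.1 admits adults from age 18 to the Major Depression study and adds: "For the Major Depressive Disorder feasibility study, all participants will be required to be categorized as Sedentary".

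On blood pressure, section 1.3 describes the measurement under the heading that covers the RCT and the feasibility studies: "Blood pressure will be assessed according to the recommendations of the American Heart Association". In the section 7.2 schedules for the feasibility studies, only the Older Adult table has the row "Blood Pressure (in-person)". The table shared by the Adolescent and Major Depression studies has no such row, although it marks a set of measures with the footnote "Measure is specific to the Major Depressive Feasibility Study". Section 7.2.6 describes the initial in-person visit for those two studies ("At the initial in-person visit, they will provide an explanation about how and when to wear the accelerometer") and mentions no blood pressure reading.

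**The concern.** A permission rule based on a count of cardiac risk factors should become stricter, or at least no looser, as the count rises. This one has an upper bound and nothing above it, so the highest possible count is handled like the lowest.

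At stake is participant safety in an exercise programme. Section 2.2 reports that in the pilot at least 88% of time was in the moderate-vigorous range and 24% in the vigorous range. Section 11.0 lists heart attack and a fatal event among the possible harms of exercise.

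The Major Depression study is where this could matter. It has no stated upper age limit, and the count rule is its only numeric cardiac criterion for entry. Section 7.2.6 gives the RCT and the Older Adult study a blood pressure and heart rate check before any research activity, with a stop above 160 systolic, 100 diastolic or 120 bpm. It describes no such check for the Major Depression study.

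**Working it through.** No sample size, power or error rate is involved, and the plan states no figure to reproduce. The check applies the written rule to each possible count.

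**Inputs**

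- Permission range: 2 to 4 of 5 factors (sections 3.2 and 7.2.5).
- Exclusion by count in the feasibility list: none (section 3.2, Feasibility Study).
- Sedentary status: required for entry (section 3.1), so every participant already has one factor and the possible counts are 1 to 5.
- Comparator: the RCT list in section 3.2 uses the same 2-to-4 permission range and separately excludes anyone with four or more factors.

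**The rule by count** (the last two columns are for the Adolescent and Major Depression studies)

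| Factors | RCT | Feasibility, as written | Feasibility, with a bound of two or more |
|---|---|---|---|
| 1 | no permission on count | no permission on count | no permission on count |
| 2 | permission | permission | permission |
| 3 | permission | permission | permission |
| 4 | in the permission range, and excluded | permission | permission |
| 5 | excluded | **no permission on count, not excluded** | permission |

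As written, permission is required at 3 of the 5 possible counts (2, 3, 4). With a bound of two or more it is required at 4 of 5 (2, 3, 4, 5). The two rules differ only at count 5.

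**The same check by combination of factors.** With sedentary status fixed, the other four factors can be present or absent in 2^4 = 16 ways.

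- Count 1: C(4,0) = 1 combination
- Count 2: C(4,1) = 4
- Count 3: C(4,2) = 6
- Count 4: C(4,3) = 4
- Count 5: C(4,4) = 1

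Permission is required for 4 + 6 + 4 = 14 of the 16. The two left out are the one with the fewest factors and the one with the most. These are counts of patterns, not of people. The documents give no prevalence, so the number of participants affected cannot be estimated.

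**Which studies are exposed**

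- *Older Adult:* section 7.2.5 sends a permission form to the provider before baseline with no count condition. This study is outside the point.
- *Adolescent:* at ages 10 to 12, all five factors together is improbable.
- *Major Depression:* the rule applies as written. This is the practical exposure, in up to 50 participants (section 8.1).

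**Whether another provision settles the case of five factors**

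- Section 3.2, disease history and PAR-Q items: not met merely by having the five factors.
- Section 4.4, phone screening by "research staff who will read the phone screening document which will ensure eligibility and will inform them of study procedures": the screener is not in the documents, so its bound cannot be checked.
- Section 6.2.3: provider permission is sought when screener answers on symptoms and medical history suggest possible harm. This is not numeric.
- Section 3.3.1: the Principal Investigator may remove anyone at discretion. This is not an entry rule.
- Section 5.2.2 (no maximal test, effort raised slowly over the first 4 to 6 weeks) and section 11.0 (CPR-trained session leaders with an emergency kit): these reduce risk but do not decide eligibility.

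None of them says what to do at five.

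**The case against.** The strongest reply has four parts.

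*The case is rare and the safeguards are layered.* The point concerns up to 50 people in a single-group study that already excludes heart disease, diabetes, stroke and PAR-Q symptoms, and five of five would be unusual among them. This stands and limits the weight of the point. It does not supply a reason for sending a two-factor person to a provider and not a five-factor person.

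*Section 6.2.3 already gives an answer.* High blood pressure and high cholesterol are medical history, so sensible staff would ask for permission anyway, and the unseen screener may say so. That is possible. But section 6.2.3 is a general statement in the HIPAA part of the protocol, and staff building a screener from the eligibility text would find 2 to 4.

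*The missing blood pressure check is a separate matter.* A person counted at five is already known to have high blood pressure, so the absent reading neither creates nor hides the gap. That is correct about its cause. The reading is relevant only as a backstop: the RCT and Older Adult visits would stop someone above the limits on the day, and the Major Depression visit as described would not.

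*The missing text may be an exclusion.* The RCT pairs the same range with an exclusion at four or more, which suggests that the upper exclusion was not carried across. If so, widening the permission range is more lenient than what was meant. This stands as an alternative remedy, and the choice belongs to the study team. Under either reading the current text is wrong at five.

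**Conclusion.** The point holds. In the Adolescent and Major Depression feasibility studies, the permission rule as written omits the highest possible count, and no count-based exclusion covers it. The error affects exactly one count, five of five. It is of practical interest only in the Major Depression study, and the number of people concerned is probably small but cannot be estimated from the documents.

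The conclusion rests on the literal text of sections 3.2 and 7.2.5 and assumes that the phone screener follows that text. If the screener already uses two or more, or excludes at five, the exposure disappears in practice and only the wording needs correcting. It looks like a drafting slip. Because it sits in a cardiac safety rule, it should be corrected, but it does not threaten the trial's results.

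**What to change.** In section 3.2 (Feasibility Study) and in section 7.2.5 (Adolescent, Major Depression), replace the 2-to-4 range with *2 or more risk factors*. Keep the consequence that section 3.2 already gives for 2 to 4: a provider's refusal excludes the person. Then confirm that the phone screener uses the same bound.

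If the study team prefers to exclude at the top, it can state that instead. Copying the RCT's exclusion at four or more would require the permission range to become 2 to 3, to avoid an overlap at four.

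The cost of the main change is wording in two places and one check of the screener. Nobody with one to four factors is treated differently. A five-factor person would need permission, and eligibility changes only if the provider refuses it.

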### **7.2.6 Visit 1 – Baseline Visit.**

#### Focus Groups

60 minute small focus group discussions will be held in a community location (e.g., library, church), at a Penn State Hershey site, or via online Zoom. One of the research staff will facilitate the focus group and it will be audio recorded for data analysis. The facilitator will review the Summary Explanation of Benefits form with the subject(s) and ask individually if they have any questions. The facilitator will use the focus group/interview guide to lead the discussion/interview. The focus group guide will include the following: (1) How best to design the playfit intervention? (2) How best to interest potential participants? (3) What concerns exist

about participating? and (4) How to design a recruitment plan?

